**Table 1: SF-36 8 Dimensions and Component Items**

| Domain                    | Individual Item                        |
|---------------------------|--|
| Physical Functioning (PF) | 3a, 3b, 3c, 3d, 3e, 3f, 3g, 3h, 3i, 3j |
| Role-Physical (RP)        | 4a, 4b, 4c, 4d                         |
| Body Pain (BP)            | 7, 8                                   |
| General Health (GH)       | 1, 11a, 11b, 11c, 11d                  |
| Vitality (VT)             | 9a, 9c, 9g, 9i                         |
| Social Function (SF)      | 6, 10                                  |
| Role-Emotional (RE)       | 5a, 5b, 5c                             |
| Mental Health (MH)        | 9b, 9c, 9d, 9f, 9g                     |

**Table 2 Transformation of SF-36 items to a scale from 0 to 100**

| Question # (Appendix 2)                              | Self-perceived health |              |
|--|-----------------------|--------------|
|  | 0 (Poor)              | 100 (Better) |
| 1, 2, 6, 8, 9a, 9d, 9e, 9h, 11b, 11d                 | 5                     | 1            |
| 3a to 3j   | 1                     | 3            |
| 4a to 4d, 5a to 5c, 9b, 9c, 9f, 9g, 9i, 10, 11a, 11c | 1                     | 5            |
| 7  | 6                     | 1            |

Programming note: Once transformed – the items should each span the range 0 to 100.

Item scores for each dimension are coded, summed, and transformed to a scale from 0 to 100, with higher scores indicating better self-perceived health (See detail in [Appendix 1](#) and [Appendix 2](#)). The calculation of the normalized domain scores relative to the original item response is presented in [Appendix 3](#). The score for each domain ranges from 0 to 100. In addition to the domain scores described above, standardized and norm-based scores are calculated for each domain. The formulae are given below.

| Domain               | Standardization (Z-score)        | Norm-Based Score |
|----------------------|----------------------------------|------------------|
| Physical functioning | $PF\_Z = (PF-83.29094)/23.75883$ | $50+10*PF\_Z$    |
| Role-physical        | $RP\_Z = (RP-82.50964)/25.52028$ | $50+10*RP\_Z$    |
| Bodily pain          | $BP\_Z = (BP-71.32527)/23.66224$ | $50+10*BP\_Z$    |
| General health       | $GH\_Z = (GH-70.84570)/20.97821$ | $50+10*GH\_Z$    |
| Vitality             | $VT\_Z = (VT-58.31411)/20.01923$ | $50+10*VT\_Z$    |
| Social functioning   | $SF\_Z = (SF-84.30250)/22.91921$ | $50+10*SF\_Z$    |
| Role-emotional       | $RE\_Z = (RE-87.39733)/21.43778$ | $50+10*RE\_Z$    |
| Mental health        | $MH\_Z = (MH-74.98685)/17.75604$ | $50+10*MH\_Z$    |

Note: Standardization is based on the 1998 general United States population.

SF-36 physical and mental component transformed scores are calculated using the conventions described below.

| Score                        | Calculation  |
|------------------------------|--|
| Aggregate Standardized Score |  |
| Physical component           | $AGG\_PHYS = (PF\_Z * 0.42402) + (RP\_Z * 0.35119) + (BP\_Z * 0.31754) + (GH\_Z * 0.24954) + (VT\_Z * 0.02877) + (SF\_Z * -0.00753) + (RE\_Z * -0.19206) + (MH\_Z * -0.22069)$ |

| Score                        | Calculation  |
|------------------------------|--|
| Aggregate Standardized Score |  |
| Mental component             | $\text{AGG\_MENT} = (\text{PF\_Z} * -0.22999) + (\text{RP\_Z} * -0.12329) + (\text{BP\_Z} * -0.09731) + (\text{GH\_Z} * -0.01571) + (\text{VT\_Z} * 0.23534) + (\text{SF\_Z} * 0.26876) + (\text{RE\_Z} * 0.43407) + (\text{MH\_Z} * 0.48581)$ |
| Transformed Summary          |  |
| Transformed physical         | $\text{PCS} = 50 + (\text{AGG\_PHYS} * 10)$  |
| Transformed mental           | $\text{MCS} = 50 + (\text{AGG\_MENT} * 10)$  |

For each of the 8 dimensions, if less than 50% of the items which constitute that dimension are missing, the dimension score will be calculated by the mean of the available non-missing items. The physical health composite summary (PCS) and mental health composite summary (MCS) will only be calculated if a score has been calculated for all 4 dimensions that constitute the composite summary.

The physical component score (PCS) includes 4 domains of the SF-36: (1) physical functioning (PF); (2) role limitations due to physical health problems (RP); (3) bodily pain (BP) and (4) general health perceptions (GH); while the mental component score (MCS) includes the other 4 domains. The mean change in these endpoints at weeks 12, 20, and 24 will be summarized by treatment group with descriptive statistics.

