***Thank you for completing these questions!***

### APPENDIX 3. SF-36 V2 SCORING ASSIGMENT

| Scale                | Item   | Coding  | Range of Raw Score | Normalized Score*      |
|----------------------|--|---|--------------------|------------------------|
| Physical functioning | Items 3a to 3j                            | Yes, limited a lot = 1
Yes, limited a little = 2
No, not limited = 3  | 10-30              | $(S-10)/20 \times 100$ |
| Role-physical        | Items 4a to 4d                            | All of the time = 1
Most of the time = 2
Some of the time = 3
A little of the time = 4
None of the time = 5                                       | 4-20               | $(S-4)/16 \times 100$  |
| Bodily pain          | Item 7                                    | None = 6
Very mild = 5.4
Mild = 4.2
Moderate = 3.1
Severe = 2.2
Very severe=1  | 2-12               | $(S-2)/10 \times 100$  |
|                      | Item 8 if both items 7 and 8 are answered | Not at all and item7 equals 'None' = 6
Not at all and item7 not equal 'None' = 5
A little bit = 4
Moderately = 3
Quite a bit = 2
Extremely = 1 |                    |                        |

| Scale          | Item                                    | Coding   | Range of Raw Score | Normalized Score*     |
|----------------|---|--|--------------------|-----------------------|
|                | Item 8 if item 7 is not answered | Not at all = 6
A little bit = 4.75
Moderately = 3.5
Quite a bit = 2.25
Extremely = 1     |                    |                       |
| General health | Item 1                           | Excellent = 5
Very good = 4.4
Good = 3.4
Fair = 2
Poor = 1                               | 5-25               | $(S-5)/20 \times 100$ |
|                | Items 11a and 11c                | Definitely true = 1
Mostly true = 2
Don't know = 3
Mostly false = 4
Definitely false = 5 |                    |                       |
|                | Items 11b and 11d                | Definitely true = 5
Mostly true = 4
Don't know = 3
Mostly false = 2
Definitely false = 1 |                    |                       |

| Scale              | Item                   | Coding  | Range of Raw Score | Normalized Score*     |
|--------------------|------------------------|---|--------------------|-----------------------|

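### SF-36v2 scoring: the item transformation in SAP section 9.4.1, Table 2 conflicts with the Appendix 3 recoding for Bodily Pain (and for General Health if read as equal steps), and nothing says which governs

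*SAP*

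**What the plan says.** Section 9.4.1 of the SAP describes SF-36v2 scoring in three places.

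- **Table 2**, headed "Table 2 Transformation of SF-36 items to a scale from 0 to 100", gives two end points per group of items. The row "1, 2, 6, 8, 9a, 9d, 9e, 9h, 11b, 11d" runs from response 5 (0) to response 1 (100). Item 7 runs from response 6 (0) to response 1 (100). The programming note adds that, once transformed, "the items should each span the range 0 to 100".
- **The text after Table 2** says: "Item scores for each dimension are coded, summed, and transformed to a scale from 0 to 100". It continues: "The calculation of the normalized domain scores relative to the original item response is presented in" Appendix 3. That appendix codes item 7 as "None = 6 Very mild = 5.4 Mild = 4.2 Moderate = 3.1 Severe = 2.2 Very severe=1". Item 8 depends on item 7: "Not at all and item7 not equal 'None' = 5", against 6 when item 7 is *none*. Item 1 is coded 5, 4.4, 3.4, 2, 1. The codes are summed to S, and the domain score is (S−2)/10 × 100 for Bodily Pain and (S−5)/20 × 100 for General Health.
- **The missing-item rule**, placed after the component-score formulas, says that if fewer than half of a dimension's items are missing, "the dimension score will be calculated by the mean of the available non-missing items".

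No sentence says how Table 2 relates to Appendix 3, or which coding the missing-item mean uses.

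**The concern.** The standardisation formulas in section 9.4.1 take one Bodily Pain score and one General Health score per subject and visit, and compare them with fixed population constants. If two programmers can reach different domain scores from the same answers, the norm-based scores, PCS and MCS are not reproducible from the plan. The weights in PCS are not small: 0.31754 for Bodily Pain and 0.24954 for General Health.

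The missing-item rule adds a second problem. A mean of Appendix 3 codes for General Health lies between 1 and 5, so it is not a 0–100 score. A mean of Table 2 items is. Taken literally, the missing-item rule fits only Table 2, while a fully answered questionnaire is sent to Appendix 3. A subject who is complete at baseline and misses a General Health item at Week 12 could have the two visits scored by different rules, and the change score would carry the difference.

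**Working it through.** **Inputs.** Table 2 end points, Appendix 3 codes and formulas, and the section 9.4.1 constants: Bodily Pain SD 23.66224, General Health SD 20.97821, and the PCS weights above. The copy of the questionnaire at hand does not show the response options for items 7 and 8, so their order is taken from Table 2 and Appendix 3.

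**Appendix 3 reproduces its own ranges.** Bodily Pain: S = 2 gives 0 and S = 12 gives 100. General Health: S = 5 gives 0 and S = 25 gives 100.

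**Step 1: item 8 alone, no interpolation.** *Not at all* with item 7 other than *none*:
- Table 2: 100, a printed end point.
- Appendix 3: code 5 on a 1–6 scale, so (5−1)/(6−1) × 100 = 80.

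**Step 2: Bodily Pain from printed end points only, items averaged.** Four answer pairs use end points for both items, and only one of them differs. For very severe pain with *not at all*:
- Table 2: (0 + 100)/2 = 50.
- Appendix 3: (1 + 5 − 2)/10 × 100 = 40.
- Difference: +10.

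**Step 3: Bodily Pain with equal steps assumed.** With r the printed response number, item 7 = 100(6−r)/5, item 8 = 100(5−r)/4, and the domain is their mean. Of the 30 answer pairs, 22 score higher under Table 2, 5 score lower and 3 agree. Examples:

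| Item 7 / item 8 | Table 2 | Appendix 3 | Difference |
|---|---|---|---|
| Very severe / not at all | 50 | 40 | +10 |
| Mild / not at all | 80 | 72 | +8 |
| None / a little bit | 87.5 | 80 | +7.5 |
| Moderate / a little bit | 57.5 | 51 | +6.5 |
| Very mild / not at all | 90 | 84 | +6 |
| Very mild / extremely | 40 | 44 | −4 |

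For example, mild / not at all is (60 + 100)/2 = 80 against (4.2 + 5 − 2)/10 × 100 = 72.

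**Step 4: General Health with equal steps assumed.** Item 1 *very good* is 75 against (4.4−1)/4 × 100 = 85. *Good* is 50 against (3.4−1)/4 × 100 = 60. Each 10-point item gap is 10/5 = 2 domain points, with Table 2 lower. The other three answers give no difference. With only three of the five items answered (40% missing, so the rule applies), the gap is 10/3 = 3.3.

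**Step 5: other domains.** Physical Functioning, Role-Physical, Vitality, Social Functioning, Role-Emotional and Mental Health give the same score either way, provided the same items are used.

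**Step 6: carried to the reported scales.**
- 8 Bodily Pain points: 8/23.66224 × 10 = 3.4 norm-based; × 0.31754 = 1.07 on PCS.
- 10 Bodily Pain points: 4.2 norm-based; 1.34 on PCS; with the MCS weight of −0.09731, −0.41 on MCS.
- 2 General Health points: 2/20.97821 × 10 = 0.95 norm-based; × 0.24954 = 0.24 on PCS.

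**The case against.** The best defence is that the SAP already gives the two tables different jobs. Table 2 is about items. The sentence on domain scores points to Appendix 3, and coding, summing and transforming is the Appendix 3 method. Table 2 even lists item 2, which belongs to no domain, so it may be only a display of item direction. The section also commits to the standard scoring algorithm. Much of this stands. A reader might infer that the SAP puts forward two equal, rival scoring rules. It does not, because the domain calculation is assigned to Appendix 3.

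Second, Table 2 prints end points only. For items 1 and 7, Appendix 3 has the same end points and could be read as supplying the values between them. That also stands: the General Health gap and all the intermediate Bodily Pain examples need the equal-step reading, which is natural but not written. It does not remove the item 8 conflict, where a printed end point in Table 2 is contradicted.

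Third, the mean of items is a missing-data provision, not the rule for complete data. It also cannot rescue a half-answered Bodily Pain scale, because one of two items is 50%, not less. This is right. The provision still has to produce a 0–100 score for General Health, and it does so directly only with Table 2-type items.

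**Conclusion.** The point holds as a minor inconsistency. The unqualified programming note and Table 2 disagree with Appendix 3, and no sentence gives precedence. Three levels of assumption should be kept apart:

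- **No assumption:** item 8 is worth 100 in one place and 80 in the other.
- **Table 2 items averaged:** Bodily Pain can differ by 10 points on the printed end points, for a pair of answers that few subjects would give.
- **Equal steps as well:** Bodily Pain differs by −4 to +10, with +6 to +8 for plausible answers such as very mild or mild pain without interference. General Health differs by 2 for two of the five item 1 answers and by nothing otherwise.

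A reader might infer that Bodily Pain would routinely be off by 10 points, or that treatment conclusions are at risk. The documents support neither. The SF-36v2 is listed as exploratory and is summarised descriptively, without modelling. Part of a same-direction shift would cancel in change from baseline when both visits are scored alike. The effect is confined to Bodily Pain, General Health, PCS and MCS, and the primary haemoglobin result is untouched.

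**What to change.** In section 9.4.1:

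1. Delete Table 2 and its programming note, or relabel the table as showing item direction only.
2. State that all eight domain scores come solely from the Appendix 3 codes and formulas.
3. Reword the missing-item rule so that the mean is taken on Appendix 3 codes before normalising: S = (mean of the available recoded items) × (number of items in the domain), then the Appendix 3 formula. With complete data this returns the ordinary score.
4. In the same edit, reconcile the less-than-50% condition with the Appendix 3 coding of item 8 when item 7 is unanswered. As written, that coding can never be used, because one of two items missing is exactly 50%.

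The cost is a change of SAP wording, with no new data.

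### The SF-36 component scores are conditioned on 4 domains although their formulas need all 8, and the missing-item rule does not fit the Appendix 3 coding for a half-answered Bodily Pain scale

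*SAP*

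**What the plan says.** SAP Section 9.4.1 fixes three things about incomplete SF-36 data.

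- **Component scores.** PCS and MCS "will only be calculated if a score has been calculated for all 4 dimensions that constitute the composite summary". On membership it says: "The physical component score (PCS) includes 4 domains of the SF-36", naming Physical Functioning (PF), Role-Physical (RP), Bodily Pain (BP) and General Health (GH). The other four, Vitality (VT), Social Functioning (SF), Role-Emotional (RE) and Mental Health (MH), go to MCS.
- **Formulas.** The same section computes PCS from the physical aggregate and MCS from the mental aggregate. Both are weighted sums of all eight domain z-scores. The non-physical part of the physical aggregate reads "VT\_Z * 0.02877) + (SF\_Z * -0.00753) + (RE\_Z * -0.19206) + (MH\_Z * -0.22069". The mental aggregate likewise carries weights on PF, RP, BP and GH.
- **Missing items.** A domain is scored from its answered items "if less than 50% of the items which constitute that dimension are missing".

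Appendix 3 has two codings for the second Bodily Pain item. One applies when both pain items are answered. The other is labelled "Item 8 if item 7 is not answered".

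**The concern.** The condition for calculating a component score and the formula that calculates it ask for different inputs. A subject with PF, RP, BP and GH scored but no MH score meets the stated condition for PCS, yet the PCS formula has a missing term. The SAP does not say what happens then. Two programmers could reasonably differ: one returns a missing PCS, the other sums the available terms. They would report different numbers of subjects and different means. If a term is dropped at one visit and present at another, the artefact goes straight into the change from baseline that is to be summarised at Weeks 12, 20 and 24.

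The second mismatch concerns Bodily Pain, which has two items. One blank item is exactly 50% missing, so the item rule gives no score. The Appendix 3 coding for item 8 without item 7 has a use only if the scale is scored from that one item.

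**Working it through.** **Inputs.** Domain means, SDs and weights are from the tables in SAP Section 9.4.1. Item counts are from that section's table of domains and component items. Codings are from Appendix 3. No missing-item rate is given. The z values and common domain scores below are assumptions for illustration.

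**1. How many domains the formulas need.** The weights are:

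| Domain | PCS | MCS |
|---|---|---|
| PF | 0.42402 | -0.22999 |
| RP | 0.35119 | -0.12329 |
| BP | 0.31754 | -0.09731 |
| GH | 0.24954 | -0.01571 |
| VT | 0.02877 | 0.23534 |
| SF | -0.00753 | 0.26876 |
| RE | -0.19206 | 0.43407 |
| MH | -0.22069 | 0.48581 |

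All eight are non-zero in each column, against the four in the stated condition. Share of absolute weight on the opposite four:

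- PCS: 0.02877 + 0.00753 + 0.19206 + 0.22069 = 0.449, of a total of 1.791, or 25%.
- MCS: 0.22999 + 0.12329 + 0.09731 + 0.01571 = 0.466, of a total of 1.890, or 25%.

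**2. What dropping a term does.** Each z-score is (domain score - population mean)/SD, so leaving a term out is the same as z = 0, the 1998 US mean. The error is -10 × weight × z. At an assumed z of -1:

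| Score | Missing domain | Error in points | Items that must be blank for the domain to be lost |
|---|---|---|---|
| PCS | MH | -10 × 0.22069 = -2.2 | 3 of 5 |
| PCS | RE | -10 × 0.19206 = -1.9 | 2 of 3 |
| PCS | SF | -10 × 0.00753 = -0.08 | 1 of 2 |
| MCS | PF | -10 × 0.22999 = -2.3 | 5 of 10 |
| MCS | BP | -10 × 0.09731 = -0.97 | 1 of 2 |

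The errors double at z = -2. The last column applies the item rule as written. The domains that one blank item can remove are those with the smaller errors.

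**3. A check with the full formulas.** Put every domain at 50 on the 0-100 scale. PCS is 40.69 with all eight domains and 37.59 with MH alone dropped, a difference of 3.10. This agrees with 10 × 0.22069 × (74.98685 - 50)/17.75604 = 3.11, up to rounding. With every domain at 75 the two values are 49.85 and 49.86, because MH is then almost at the population mean. The error depends on how far the subject is from that mean.

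**4. Scale in an arm.** The Main study plans about 95 subjects in seven stratum-by-treatment columns (three low-dose, four high-dose). If these are equal in size, 95/7 is about 14 per column. One subject with a 2.2-point error moves a column mean by about 2.2/14 = 0.16 points.

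**5. The item rule.** Largest number of blank items at which a domain is still scored:

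| Domain (items) | Less than 50% missing | At most 50% missing |
|---|---|---|
| PF (10) | 4 | 5 |
| RP (4), VT (4) | 1 | 2 |
| BP (2), SF (2) | 0 | 1 |
| GH (5), MH (5) | 2 | 2 |
| RE (3) | 1 | 1 |

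BP tolerates no blank item under the SAP's rule.

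**6. Is the Appendix 3 coding meant for use?** With item 7 blank, item 8 is coded 6, 4.75, 3.5, 2.25 or 1. Filling item 7 with the item 8 value (the mean of the answered items) gives S = 2x, and the Appendix 3 formula (S - 2)/10 × 100 gives 100, 75, 50, 25 or 0. That is an even, full-range scale, as a coding intended to score Bodily Pain from item 8 alone would give.

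**The case against.** The condition is worded as *only if*, which makes four scored domains necessary, not sufficient. The formula must still be evaluated, and with a missing z-score it naturally returns a missing value. Section 9.4.1 also refers scoring to a published manual, which may settle the matter and is not at hand. This stands. A reader might infer that the SAP prescribes a silent imputation at the population mean. It does not: nothing tells the programmer to drop a term or set z to 0. Nor do both readings mix differently built scores. If the composite is simply missing, nothing is mixed. What remains is that under the strict reading the four-domain condition does no work, since all eight are always required, while a programmer who takes it at face value has to drop terms.

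A reader might also extend the Appendix 3 conflict to every domain that the 50% threshold can remove. The documents do not support that. A half-answered SF, RP or VT is left unscored too, but Appendix 3 has no coding for those cases, so nothing is contradicted. Even for Bodily Pain, the item rule says what happens below 50% and is silent at exactly 50%, so the Appendix 3 branch could be read as the specific rule for that scale. That reading is possible, but the SAP does not state it.

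Finally, the larger errors need several blank items in one domain, and the SAP gives no rate of missing items. No effect on an arm mean is shown beyond the one-subject illustration.

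**Conclusion.** Both mismatches are real and can be seen in the SAP alone. The condition for PCS and MCS names four domains where the formulas need eight. The item rule, read in the ordinary way, leaves Bodily Pain unscored in the very case for which Appendix 3 supplies a coding.

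The possible error is about 2 points per affected subject for MH or RE in PCS or PF in MCS, and 1 point or less for the domains that a single blank item removes. This rests on an assumed z of -1 and on a program that drops missing terms, which the SAP neither instructs nor excludes. The Appendix 3 conflict is shown for Bodily Pain only.

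Severity is minor. SF-36 sits under the exploratory endpoints, is summarised descriptively, and is affected only where questionnaires are incomplete.

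**What to change.** 1. Replace the four-domain condition in Section 9.4.1 with a statement that PCS and MCS are calculated only when all eight domain scores are available, and are otherwise missing.
2. Reconcile the missing-item rule with the Appendix 3 Bodily Pain coding. The preferred change is to score a domain when at least 50% of its items are answered. This also raises the tolerance by one blank item in SF, RP, VT and PF, and leaves GH, RE and MH unchanged. The narrower alternative is to keep the threshold and make the item 8 coding an explicit exception for Bodily Pain.

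The cost is two sentences and a check of the scoring program, with no new data. The downside is that a few component scores become missing compared with a program that sums the available terms. Bodily Pain scores regained under the second change partly offset this. Under the preferred threshold some domain scores will rest on half of their items.

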#### 9.4.2 Patient Global Impression of Severity (PGI-S)

The patient global impression of severity (PGI-S) includes 2 questions with the patient response score of 0 (no impact at all) to 10 (as bad as it can be):

1. How would you rate the impact of your anemia and its treatment on how you feel?
2. How much does the treatment you currently take for anemia help you daily activities?

The change from baseline in PGI-S will be summarized by treatment group with descriptive statistics including the number of subjects, mean, median, standard deviation and range.

